10.6.8.1.10. Diagnosis Versus Signs or Symptoms

In general, the use of a unifying diagnosis is preferred to the listing out of individual symptoms. Grouping of symptoms into a diagnosis should only be done if each component sign and/or symptom is a medically confirmed component of a diagnosis as evidenced by standard medical textbooks. If any aspect of a sign or symptom does not fit into a classic pattern of the diagnosis, report the individual symptom as a separate AE.

10.6.8.1.11. Reporting Serious Adverse Events

All SAEs are subject to reporting requirements.

10.6.8.1.12. Serious Adverse Events

All SAEs, whether or not considered related to study drug, must be immediately reported to Pfizer Safety on the CT SAE Report Form upon awareness **and under no circumstances should the time to report exceed 24 hours of becoming aware of the event.**

If additional follow-up information is required or becomes available for a previously reported SAE, entry into eCRF of the new or updated information should be completed and reported to Pfizer Safety on a new CT SAE Report Form **within 24 hours of awareness.**

Elective hospitalization and/or surgery for clearly preexisting conditions (eg, a surgery that has been scheduled prior to the subject's entry into the study) will not be reported as an SAE.

Any SAE that is ongoing when the subject completes the study or discontinues the study will be followed by the Investigator until the event resolves, stabilizes or returns to baseline status.

10.6.8.1.13. Serious, Unexpected Adverse Drug Reactions

All ADRs that are both serious and unexpected are subject to expedited reporting to regulatory agencies and will be reported in accordance with Directive 2001/20/EC or as per national regulatory requirements in participating countries. An unexpected ADR is one for which the nature or severity is not consistent with information in the relevant source documents.

The following documents or circumstances will be used to determine whether an AE/ADR is expected:

5. For a medicinal product not yet approved for marketing in a country, the reference safety information section of a company's IB will serve as the source document in that country
6. Reports that add significant information on specificity or severity of a known, already documented serious ADR constitute unexpected events. For example, an event more specific or more severe than described in the reference safety information in the IB would be considered "unexpected."

10.6.9. Pregnancy and Lactation

Pregnancy

If at any point any pregnancy test is positive, the subject will be withdrawn from the study drug.

Details of all pregnancies in female subjects and female partners of male subjects will be collected after the start of study treatment and until 30 days after the last dose.

Pregnancy (during maternal or paternal exposure to study treatment) does not meet the definition of an AE; however, to fulfill regulatory requirements, any pregnancy and/or pregnancy outcome should be reported to Pfizer Safety via the CT SAE Report Form and the EDP Supplemental Form **within 24 hours of awareness.**

- Abnormal pregnancy outcomes (eg, spontaneous abortion, fetal death, stillbirth, congenital anomalies, ectopic pregnancy) are considered SAEs and should be reported as such (following the SAE reporting process) even if outside the SAE reporting period. Examples of environmental exposure may include oral ingestion of, inhalation of, or skin contact with a tablet that is broken/crushed.

Any such exposures to the study drug under study are reportable to Pfizer Safety within 24 hours of investigator awareness irrespective of whether an AE has occurred.

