8.2. Reasons for Discontinuation from the Study

The reason(s) for study discontinuation must be determined by the Investigator and recorded in the source documents and on the eCRF. If a subject discontinues for more than 1 reason, each reason should be documented in the source document and the most clinically relevant reason should be entered on the eCRF.

- AE
- Withdrawal by subject
- Study termination by Sponsor
- Pregnancy
- Non-compliance
- Lost to follow-up

- Lack of efficacy
- Death
- Other

All patients should be encouraged to complete the study. However, a subject may elect to discontinue study participation at any time for any reason without prejudice to their future medical care by the physician or the institution. If a subject withdraws consent, no further evaluation should be performed, and no additional data should be collected. The Sponsor may retain and continue to use any data collected before such withdrawal of consent. The Investigator should make a reasonable attempt to document the specific reason why consent was withdrawn and date of last study drug intake.

Subjects who discontinue treatment prematurely, regardless of the reason, should be instructed to return for an Early Termination and Follow-Up Visits. Refer to Section 9.6 and Section 9.5 for description of ET and follow-up procedures, respectively.

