10.3.5. Pregnancy Testing

The following instructions on pregnancy testing apply to all WOCBP. Women who are surgically sterile or who are postmenopausal are not considered to be of child-bearing potential. Postmenopausal is defined as 12 consecutive months with no menses without an alternative medical cause and confirmed by an FSH level in the postmenopausal range. In the absence of 12 months of amenorrhea, a single FSH measurement is insufficient to confirm postmenopausal state.

At Screening a serum pregnancy test for β -hCG will be performed to determine eligibility. On Day 1, urine pregnancy test must be performed and negative pregnancy must be documented prior to dosing.

After Day 1, urine pregnancy tests (β -hCG) should be performed monthly either at home per country-specific guideline or at the study site and documented in the eDairy or eCRF. Monthly home urine pregnancy tests will be supplied to subjects as needed. Negative pregnancy test results for the respective month must be verified prior to in-person dosing for Hybrid Visits. Visual inspection of the pregnancy test result via videoconferencing is recommended for virtual assessments and it should be documented. Subjects should be instructed to immediately report any positive result to the study site, and the subject will have study treatment interrupted and a serum sample will be submitted to the central laboratory for β -hCG testing. If the serum test confirms positive, the subject will be discontinued from the study treatment and all the necessary follow-up will be conducted as per Section 10.6.9. If the serum test is negative, the subject may resume study treatment.

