
Pregnancy and Postmenopausal Status Testing Serum pregnancy test for β-hCG (Screening or if positive urine pregnancy test; WOCBP only) Urine pregnancy test for β-hCG (Day 1 and monthly post-Day 1; WOCBP only) FSH (Screening; postmenopausal women only)
	

CBC with Differentials Hematocrit Hemoglobin Mean corpuscular hemoglobin Mean corpuscular hemoglobin concentration Mean corpuscular volume Platelet count Red blood cell count WBC^a count WBC differential count (absolute and %): lymphocytes, neutrophils, eosinophils, monocytes, basophils
	

TBNK Panel^a T, B, NK, CD4+ T cell and CD8+ T cell count (absolute number and percentage)
	

Serum Chemistry Albumin Alkaline phosphatase Alanine aminotransferase Aspartate aminotransferase Bicarbonate Blood urea nitrogen Calcium Chloride Creatinine
	
Glucose Potassium Sodium Total bilirubin Total protein

CCI
	

^a WBC count, WBC differential count, and TBNK panel will be assessed by an independent Medical Monitor during treatment (ie, after Day 1) until completion of the Double Blind Treatment Period dose selection analysis at Week 24 or subject discontinues study treatment (whichever occurs first) while the Investigators will assess the results of these lab parameters during Screening, on Day 1, and during the post treatment follow-up (refer to Section 10.6.7.2).

β -hCG, beta-human chorionic gonadotropin; CBC, complete blood count; FSH, follicle-stimulating hormone; HBsAg, hepatitis B surface antigen; anti-HBc, hepatitis B core antibody; HCV, hepatitis C virus; HIV, human immunodeficiency virus; INR, international normalized ratio; TBNK, T, B, NK, CD4+ T cell, and CD8+ T cell count (absolute number and percentage); WBC, white blood cell; WOCBP, woman of child-bearing potential

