 - ^g Safety 12-lead ECGs will be performed with the subject in the supine position prior to blood sample collection and after vital signs are measured at Screening and prior to randomization on Week 0/Day 1 (Baseline), and 4 hours (± 15 minutes) after dosing on Week 0/Day 1. At the Week 24 visit, vital signs should be measured first, followed by ECGs, predose PK sample collection, study drug dosing at the study site, and first-dose cardiac monitoring for subjects continuing in the Extension Treatment Period.
 - ^h Complete physical examination (including assessments of the skin, head, eyes, ears, nose, throat, thyroid, lungs, heart, abdomen, back, lymph nodes, extremities, body weight, and height [height collected at Week 0/Day 1 Visit only]) should be performed at Week 0/Day 1 and the ET visit.
 - ⁱ PFTs include FEV₁ and FVC measurements. Where locally available, DLCO measurements will also be performed (sites where DLCO is not available should consult the Sponsor or Sponsor's delegate). If Week 24 or ET result is abnormal, then testing should be repeated as soon as able. Post-screening PFTs may be performed within 7 days of the study visit. Details regarding additional PFTs are provided in Section 10.6.5.
 - ^j Scheduled non-screening ophthalmoscopy with OCT may be performed within 7 days of the study visit. Screening ophthalmoscopy with OCT is to be conducted with subjects' pupils dilated (Section 10.6.6).
 - ^k Only for women of child-bearing potential. Serum β -hCG test required at screening. On Day 1, urine pregnancy test must be performed and negative test result verified prior to dosing. Monthly urine pregnancy test either at home or at the study site at all other visits. Visual inspection of the test result via videoconferencing for virtual assessment is recommended. If at any point there is a positive urine β -hCG test, the subject will have study treatment interrupted and a serum sample submitted to the central laboratory for β -hCG testing (Section 10.6.9).
 - ^l Clinical laboratory tests will include serum chemistry, CBC with differentials, and coagulation. Screening samples should be obtained, and results must be available and reviewed prior to the first dose of study treatment. On other study visits, samples should be obtained prior to the daily dosing. Refer to Section 10.6.4.

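### Protocol 10.6.9 withdraws a subject from study drug after any positive pregnancy test, while 10.3.5 requires serum confirmation and lets a serum-negative subject resume (minor)

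*Protocol*

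**What the plan says.** Protocol Section 10.6.9 (Pregnancy and Lactation) gives a one-step rule: "If at any point any pregnancy test is positive, the subject will be withdrawn from the study drug". It has no confirmation step and no route back to treatment.

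Protocol Section 10.3.5 (Pregnancy Testing) gives a stepwise rule for a positive monthly urine test:

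- First, "the subject will have study treatment interrupted and a serum sample will be submitted to the central laboratory".
- Then, "If the serum test confirms positive, the subject will be discontinued from the study treatment". Only at this stage does the section point to 10.6.9, and only for follow-up.
- Otherwise, "If the serum test is negative, the subject may resume study treatment".

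The Appendix 1 schedules repeat the first step. Table 7 footnote k and Table 8 footnote j both say that after a positive urine test "the subject will have study treatment interrupted and a serum sample submitted to the central laboratory", and both cite Section 10.6.9. Table 3 (Section 10.6.4) lists the serum test for use at "Screening or if positive urine pregnancy test; WOCBP only".

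**The concern.** A woman with a positive urine test and a negative serum test gets two different instructions. Under 10.3.5 she may go back on study drug; under 10.6.9 she is withdrawn from it. A site that lets her resume contradicts 10.6.9 as written. A cautious site can satisfy both sections only by running the serum test and withdrawing her anyway, because 10.3.5 permits resumption but does not require it. The text therefore tilts towards the outcome that was probably not intended.

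What is at stake is needless loss of treatment for a non-pregnant subject and, if it happens before Week 16, probable loss of her primary-endpoint assessment. Section 8.2 says: "Subjects who discontinue treatment prematurely, regardless of the reason, should be instructed to return for an Early Termination and Follow-Up Visits". The option in Section 6.7.4 to stay in the study off treatment covers only lack of efficacy between Weeks 16 and 24.

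**Working it through.** The contradiction is textual; arithmetic is needed only for its consequence and size.

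**1. The rules side by side**

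| Test results | 10.6.9 | 10.3.5 |
|---|---|---|
| Urine positive, serum positive | Withdrawn | Interrupted, then discontinued |
| Urine positive, serum negative | Withdrawn | Interrupted, may resume |

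The sections differ only in the second row.

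**2. Could withdrawal mean a temporary hold?** Not reasonably. For a hold the protocol speaks of interruption (10.3.5, 10.6.7.2, both schedule footnotes). SAP Section 18.2.3 uses the eCRF action of drug withdrawal to identify permanent discontinuation.

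**3. Which section is the outlier?** Table 3 and both footnotes provide for a serum test after a positive urine test. That test would decide nothing about treatment if every positive already meant withdrawal. Section 10.3.5 sends the reader to 10.6.9 only after confirmation, for follow-up. Section 10.6.9 is therefore the outlier.

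**4. Does anything settle precedence?** No. The mandatory-discontinuation list in Section 8.1 does not mention pregnancy. The footnotes do not state resumption, and they point to 10.6.9, which lacks the serum step.

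**5. Would the Week 16 PEC be lost?**

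- Scheduled urine tests after Day 1 and before Week 16 are at Weeks 4, 8 and 12 (Table 7).
- Latest in-window Week 12 test: Day 85 + 5 = Day 90.
- Early Termination visit within 7 days of last dose (Section 9.6): about Day 90 + 7 = Day 97.
- The Week 16 analysis window is Days 100 to 127 (SAP Section 6.4).

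Since 97 < 100, a biopsy at an on-time Early Termination visit falls outside the Week 16 window. Her Week 16 PEC would be imputed for the primary endpoint (Protocol 11.4.1, SAP 17.1.2) and counted as nonresponse for the two responder endpoints (Protocol 11.4.1, SAP 17.2.3.2).

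**6. How many subjects?** The documents give neither the number of women of child-bearing potential nor a false-positive rate. They note a male predominance in the disease (Protocol 1.1.1). I assume 15–30 such women among about 96 subjects, a false-positive rate of 0.5–1% per urine test, and 10–50% of sites applying 10.6.9 over 10.3.5.

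Subjects exposed to the conflict before Week 16 = women × tests × false-positive rate:

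- Low: 15 × 3 × 0.005 = 0.225
- High: 30 × 3 × 0.01 = 0.90

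Subjects lost = exposed × share of sites:

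- Low: 0.225 × 0.10 = 0.02
- High: 0.90 × 0.50 = 0.45

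Weight of one loss: 96 subjects at 3:3:2 give arms of 36, 36 and 24, so one subject is 1/36 = 2.8% of an etrasimod arm or 1/24 = 4.2% of placebo.

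**The case against.** The strongest reply is that the protocol nearly resolves this itself. Section 10.3.5 is the dedicated testing section and sets out the full algorithm. The rest of 10.6.9 concerns reporting of pregnancies and exposures, so its opening sentence can be read as applying to confirmed pregnancy. Section 9.1 makes the schedules binding, and hence the serum step too. Sections 8.2 and 9.6 name pregnancy, not a positive test, as a reason for discontinuation. Section 8.1 asks sites to notify the Medical Monitor of any treatment discontinuation, which gives a chance to catch a mistake. Loss of Week 16 data is not automatic either: the 7-day target is a recommendation, and an Early Termination endoscopy delayed to Day 100 or later would count as Week 16. Finally, the frequency figures rest on assumptions.

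Much of this stands as mitigation. The intended rule can be inferred, a delayed visit after a Week 12 withdrawal could rescue the assessment, and the counts are illustrations, not bounds. The conflict remains, however. Binding sites to the serum step does not say what to do when serum is negative, because the footnotes are silent on that and refer the reader to 10.6.9. Notifying the Medical Monitor may catch the error but does not remove it. Withdrawals after a Week 4 or Week 8 test would still miss the Week 16 window at an Early Termination visit.

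**Conclusion.** The concern holds, as a minor one. Section 10.6.9 is wrong as written, and that conclusion needs none of the numerical assumptions. The practical effect is confined to urine-positive, serum-negative women at sites that follow 10.6.9 over 10.3.5. Under the assumed ranges the expected loss before Week 16 is well under one subject, so most likely none. No sample-size figure or trial conclusion depends on it. Fetal protection is the same under both rules, because each stops dosing on the positive urine test.

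**What to change.** Reword the sentence in 10.6.9 along these lines: *A positive urine test leads to interruption of study drug and a central serum test under Section 10.3.5. Study drug is withdrawn if any serum test is positive; it may be restarted under Section 10.3.5 if the serum test is negative.* This keeps withdrawal on any positive serum result.

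In Table 7 footnote k and Table 8 footnote j, cite Sections 10.3.5 and 10.6.9 together, so that the reader reaches the serum procedure and keeps the pointer to the 24-hour reporting rules.

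The cost is wording in three places. Amendments need IRB/EC approval (Section 12), so a stand-alone amendment is not justified; include the change in the next one.

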10.6.9.1. Exposure During Pregnancy

An environmental EDP occurs if:

- A female nonsubject is found to be pregnant while being exposed or having been exposed to study treatment because of environmental exposure.
- A male nonsubject who has been exposed to the study drug then inseminates his female partner prior to or around the time of exposure.

10.6.9.2. Exposure During Breastfeeding

An environmental EDB occurs if:

- A female nonsubject is found to be breastfeeding while being exposed or having been exposed to study drug.

When EDB occurs in the setting of environmental exposure, the exposure information does not pertain to the subject enrolled in the study, so the information is not recorded on a CRF. However, a copy of the completed CT SAE Report Form is maintained in the investigator site file.

10.6.9.3. Occupational Exposure

The investigator must report any instance of occupational exposure to Pfizer Safety within 24 hours of the investigator's awareness using the CT SAE Report Form, regardless of whether there is an associated SAE. Since the information about the occupational exposure does not pertain to a subject enrolled in the study, the information is not recorded on a CRF; however, a copy of the completed CT SAE Report Form must be maintained in the investigator site file.

10.6.10. Lack of Efficacy

The investigator must report signs, symptoms, and/or clinical sequelae resulting from lack of efficacy. Lack of efficacy or failure of expected pharmacological action is reportable to Pfizer Safety **only if associated with an SAE.**

10.6.11. Medication Errors

Medication errors may result from the administration or consumption of the study drug by the wrong subject, or at the wrong time, or at the wrong dosage strength. Medication errors not associated with an AE/SAE should be recorded as a protocol deviation.

A medication error with a potentially associated AE/SAE is recorded in the CRF. Medication errors associated with an SAE (per the Investigator's assessment) should be reported to Pfizer Safety within 24 hours on the CT SAE Report Form. SAEs must be reported to the designated Sponsor Contact via established reporting mechanism within 24 hours of awareness.

In the event of a medication dosing error, the sponsor should be notified within 24 hours.

Medication errors should be reported to Pfizer Safety within 24 hours on a CT SAE Report Form **only when associated with an SAE.**

10.7. Procedures for Overdose

The current edition of the IB should be referenced for overdose procedures.

There is no established overdose threshold for this clinical study, nor is there any recommended specific treatment for an overdose but to provide supportive care if clinically indicated.

In the event of a suspected overdose, the Investigator and/or treating physician should:

- Closely monitor the subject for any AE/SAE and laboratory abnormalities and follow AE reporting process, including contacting the Medical Monitor
- Obtain a plasma sample for PK analysis within 7 days from the date of the last dose of study treatment, if possible, and if requested by the Medical Monitor
- Document the total quantity of the excess dose, taking into consideration the duration of the overdose in the eCRF and the time frame

Subjects who overdose will be counseled on correct dosing and administration of study treatment. Decisions regarding study discontinuation, dose interruptions, or dose modifications will be made by the Investigator in consultation with the Medical Monitor based on the clinical evaluation of the subject.

10.8. Genetic Testing

Genetics may be evaluated in this study to assess genetic variation that may impact response to treatment, metabolism, and mechanism of action of etrasimod and for consideration of risks of the disease state.

A blood sample for DNA isolation will be collected from subjects who have consented to participate in the genetic analysis component of the study. Participation is optional. Subjects who do not wish to participate in the genetic research may still participate in the study.

In the event of DNA extraction failure, a replacement genetic blood sample may be requested from the subject. An additional ICF may be provided to subjects for genetic analyses. Signed informed consent will be required to obtain a replacement sample unless it was included in the original consent.

Details on processes for collection and shipment and destruction of these samples are provided in the Laboratory Manual.

CCI [Redacted]

[Redacted]

- [Redacted]
- [Redacted]

[Redacted]

[Redacted]

CCI [Redacted]

[Redacted]

[Redacted]

- [Redacted]
- [Redacted]
- [Redacted]

[Redacted]

[Redacted]

CCI [REDACTED]

[REDACTED]

[REDACTED]

[REDACTED]

10.10. Qualitative Interview

Qualitative interviews may be conducted with a subset of subjects who have consented to participate in the Qualitative Interview component of the study. Participation is optional. Subjects who do not wish to participate in the Qualitative Interview may still participate in the study.

The Qualitative Interview will gather insights about subjects' symptom experience during the study and identify any additional aspects of change that might be important to assess for future studies. Other factors driving subject satisfaction with treatment and perceptions on meaningful change will be asked.

The Qualitative Interview will be conducted via telephone by a trained qualitative research interviewer using a semi-structured interview guide. All interviews will be conducted in the participant's native language and will be audio recorded in accordance with applicable laws of the jurisdictions where the subjects are located. The audio recording will be transcribed for analysis and will be destroyed after evaluation. Interviews will be conducted within 14 days after the Week 24 visit. Failure to complete the optional interview that a subject has consented to will not constitute a protocol deviation. If a potential adverse event is discovered during the interview process, the information will be shared by the interviewer with the Investigator.

